### 10.7.7. Reporting of AESIs

#### **AESI Reporting**

- AESIs must be reported to the sponsor within 24 hours of awareness of the event by completing the appropriate eCRF and notifying Allergan study management personnel and the Medical Safety Physician by fax or email.
- Contacts for SAE reporting can be found on the protocol title page.
- Allergan will notify the FDA of any AESI within 10 days of Allergan's awareness of the event.

### 10.7.8. AE, ADE, SAE, SADE Determination Flow Chart

Adverse event reporting for countries other than the United States and European Union must follow the regulatory and ethical requirements for that country.

# **10.8.** Appendix 8: Amendment 1 Summary of Changes

### Amendment 1 (January 2020)

### **Overall Rationale for the Amendment:**

#### Minor clarifications

| Section # and Name   | Description of Change  | Brief Rationale  |
|--|--|---|
| Table 1-6 Control Group
Procedures: Delayed
Treatment Period | Added to footnote d that a urine pregnancy test is
among the assessments to be conducted for
participants exiting the study prior to Month 6 | To provide for pregnancy testing prior to study exit                      |
| 5.2 Exclusion Criteria   | Corrected exclusion criterion 4.02 to remove
"not" and corrected numbering of exclusion
criteria   | To correct typo and formatting  |
| 8.1.3 Secondary
Effectiveness Measures                          | Changed GAIS assessments from profile view
photographs to frontal and lateral view
photographs   | To allow more complete
views of the temple area in
GAIS assessments |

1.0 Introduction

This Statistical Analysis Plan (SAP) provides a technical and detailed elaboration of the statistical analyses of the effectiveness and safety data as outlined and specified in the final protocol of Study 1878-702-008 (Amendment 2, 12 May 2021). Specifications of tables, figures and data listings are contained in a separate document.

2.0 Study Design and Objectives

2.1 Study Objectives

[figure not shown]
The objectives of this study are to evaluate the safety and effectiveness of VOLUMA XC injectable gel in adult participants seeking correction of temple hollowing.

2.2 Study Design Overview

This is a prospective, multicenter, evaluator-blinded, randomized, parallel-group, controlled study to evaluate the safety and effectiveness of VOLUMA XC injectable gel to correct temple hollowing. See protocol Section 4.1 Overall Design for details.

The schematic of the study is shown in Figure 1.

Figure 1. Study Schematic

2.3 Treatment Assignment and Blinding

Subjects will be randomized to VOLUMA XC group or control group in a 2:1 ratio based on a [REDACTED]

[REDACTED]

[REDACTED]

[REDACTED]

[REDACTED]

[REDACTED]

[REDACTED]

[REDACTED]

[REDACTED]

3.0 Endpoints

3.1 Primary Endpoint(s)

Primary endpoint is ATHIS responder status at Month 3.

3.2 Secondary Endpoint(s)

Secondary endpoints are:

- Responder status for EI assessment of GAIS in the temple area at Month 3
- Responder status for participant assessment of GAIS in the temple area at Month 3
- Change from baseline in participant responses to FACE-Q Satisfaction with Facial Appearance questionnaire, for the Rasch-transformed score (0-100) at Month 3
- Change from baseline in participant responses to FACE-Q Satisfaction with Temples questionnaire, for the Rasch-transformed score (0-100) at Month 3

3.3 Other Effectiveness Endpoint(s)

[REDACTED]

[REDACTED]

[REDACTED]

[REDACTED]

[REDACTED]

[REDACTED]

[REDACTED]

[REDACTED]

[REDACTED]

[REDACTED]

3.4 Safety Endpoint(s)

The safety endpoints will include procedural pain, ISRs, AEs, jaw function assessment, Snellen visual acuity, confrontational visual fields, ocular motility, and concomitant medications and procedures.

3.5 Additional Endpoint(s)

Not applicable.

4.0 Analysis Populations

The analysis populations will consist of participants as defined in Table 1 below:

Table 1. Analysis Sets

Population	Definition	Study Intervention
mITT	All randomized participants who have non-missing baseline assessment on the AHS for both temples. This will be used as the full-analysis-set population.	As randomized
Observed Primary Endpoint (OPE)	All mITT population participants who have a Month 3 assessment on the AHS for both temples.	As randomized
Safety	All participants who are randomized and received study intervention (VOLUMA XC or no-treatment control).	As treated
VOLUMA XC Treated (VT)	All safety population participants who received VOLUMA XC treatment as initial treatment at the beginning of the Control Period, or as optional treatment after the Control Period	As treated
VOLUMA XC Maintenance Treatment (VMT)	All safety population participants who received VOLUMA XC maintenance treatment	As treated

The number of participants in each of the 5 study populations (mITT, OPE, Safety, VT and VMT) will be summarized by treatment group, if applicable.

5.0 Participant Disposition

5.1 Study Period

The study periods are defined below in Table 2 for VOLUMA XC group and control group. For VOLUMA XC group, the Treatment Period (TP) is the Control Period (CP) plus the Post-Control Period (PCP). For participants in the control group, the TP starts on the date of optional treatment and ends on the same day as the study exit.

Table 2. Definition of the Control, Treatment and Maintenance Treatment Periods by Analysis Group (as-randomized for effectiveness or as-treated for safety)

Analysis Group	Period	Analysis Group Label	Start Date	End Date
VOLUMA	CP	VOLUMA XC	Initial treatment date	
The end date is the date of the Month 3 assessment:
 
 • If multiple assessments fall into Month 3 window, the date of the assessment included in the Month 3 analysis will be used as end date. • For participants who exit before Month 3, the end date is study exit date. • For participants with a missing assessment at Month 3, the end date is the target day for Month 3 (90 days from preceding treatment).
	TP	VOLUMA XC	Initial treatment date	Date of maintenance treatment or the study exit date, whichever is earlier
	MP	VOLUMA XC	Maintenance treatment date	Study exit date
Control	CP	Control	Randomization date	
For participants who do not receive optional treatment:
 
 • If multiple assessments fall into Month 3 window, the date of the assessment included in the Month 3 analysis will be used as end date. • For participants who exit before Month 3, the end date is study exit date. • For participants with missing assessment at Month 3, the target day for Month 3 (Day 91) will be the end date. 
For participants who receive optional treatment, the end date is the date of optional treatment.

	TP	VOLUMA XC Post-Control	Optional initial treatment date	Study exit date

The start and end of treatment periods listed above for the mis-treated participants (ie., randomized to treatment and did not receive VOLUMA XC or randomized to control and was treated with VOLUMA XC prior to the primary timepoint) will be determined based on the treatment received.

For CP, effectiveness analyses and baseline characteristics will be performed on the mITT population using the "as-randomized" assignment.

For TP, effectiveness and safety summaries will be performed on the VT population by treatment group.

For MP, effectiveness and safety summaries will be performed on the VMT population.

5.2 Participant Disposition

The summary of study disposition will be done for all screened participants overall and by treatment group as randomized. Number and percentages are based on the numbers of participants in their randomized allocations will be provided for the following:

- Number of participants screened (overall)
- Number of participants randomized (this number will be used as denominator to compute the following percentages)
- Number of participants treated as randomized
- Number of participants not treated as randomized

For mITT population during CP:

- Number of participants completed CP
- Number of participants discontinued during CP
- Reasons for discontinuation during CP

For VT population during PCP:

- Number of participants who continued into PCP
- Number of participants who completed PCP
- Number of participants who discontinued during PCP
- Reasons for discontinuation during PCP

For VMT population during MP:

- Number of participants who received maintenance treatment
- Number of participants who completed MP
- Number of participants who discontinued during MP
- Reasons for discontinuation during MP

For mITT population during the study:

- Number of participants who completed the study
- Number of participants who discontinued from the study
- Reasons for discontinuation from the study

Treatment group participants who elect not to receive maintenance treatment are considered to have completed the study if they complete the Month 13 visit in the Post-Control Period. Meanwhile, treatment group participants who elect to receive maintenance treatment are considered to have completed the study if they complete the Month 6 visit in the Maintenance Period. Control group participants who elect not to receive optional treatment are considered to have completed the study if they complete the Month 3 visit in the Control Period. Meanwhile, control group participants who elect to receive optional treatment are considered to have completed the study if they complete the Month 13 visit in the Post-Control Period.

In addition, a listing will be provided for participant disposition.

6.0 Study Device Exposure and Administration

Treatment exposure-related variables will be summarized for the VT and VMT populations. For control group, data after receiving optional initial treatment at Month 3 are included. Study treatment exposure will be measured by volume injected at each treatment (Table 3) and summarized by treatment group, treatment (initial, touch-up, combined initial and touch-up, maintenance), and treatment area.

Table 3. Exposure to Study Treatment

Endpoint	Description	Timing	Methodology
Number (%) of participants received treatment	Summary by treatment group, treatment (initial, touch-up, maintenance)	Initial, Touch-up, Maintenance	Frequency counts and percentages
Number (%) of participants who did not receive maintenance	Summary by reason	Maintenance	Frequency counts and percentages
Injection volume 
 • Total • Left temple • Right temple 	Summary by treatment group, treatment (initial, touch-up, initial and touch-up combined, maintenance), and treatment area	Initial, Touch-up, Initial and Touch-up combined, Maintenance	Continuous descriptive statistics

The number of participants who received treatment anesthesia will be summarized for the VT and VMT populations by treatment group. Variables related to administration of treatment listed in Table 4 will be summarized for the VT and VMT populations by treatment group, treatment area (right and left temple area), and treatment (initial, touch-up).

7.0 Demographics, Baseline Characteristics, Medical History, and Prior/Concomitant Medications

7.1 Demographics and Baseline Characteristics

Demographic parameters (age; age group; sex; race; ethnicity) will be summarized descriptively in total and by treatment group for the mITT populations. Age (years) is calculated relative to informed consent date. For summary by race, participants who reported multiple races are only included in the 'Multiple' category.

Number (%) of participants who reported multiple races will be summarized as applicable.

Baseline characteristics shown below will be summarized descriptively in total and by treatment group for the mITT populations:

- Weight (kg), height (cm), and BMI (kg/m²)
- Fitzpatrick Skin Phototype (each phototype, and by phototype groups, i.e., I and II, III and IV, V and VI)
- Exposure to sunlight (hours per day)
- Smoking history (status, tobacco product, frequency, and duration in months)
- Allergan Temple Hollowing Scale
- FACE-Q Satisfaction with Facial Appearance questionnaire, for the Rasch-transformed score
- FACE-Q Satisfaction with Temple questionnaire, for the Rasch-transformed score
- Jaw Functional Limitation Scale
- Self-perception of age

Demographic and baseline characteristics will be provided in a listing.

7.2 Medical History

Abnormalities in participants' medical, surgical, cosmetic, and dental history, encompassing abnormalities, surgeries, and procedures reported as occurring before the Screening Visit, will be coded using the Medical Dictionary for Regulatory Activities (MedDRA). The actual version of the MedDRA coding dictionary will be noted in the statistical outputs and clinical study report.

Listing will be provided for the safety population.

7.3 Prior and Concomitant Medications

The medication data will be coded using the World Health Organization (WHO) Drug Dictionary. The actual version of the WHO Drug Dictionary will be noted in the statistical outputs and clinical study report. Prior medication is defined as any medication taken prior to the latter of randomization date or first treatment date in the control period. Concomitant medication is defined as any medication taken on or after the latter of randomization date or first treatment date in the control period.

Listing will be provided for the safety population. The Anatomical Therapeutic Chemical (ATC) class, code, and preferred drug name will be presented (i.e., 4th level, or most specific level available if 4th level is unavailable).

8.0 Effectiveness Analyses

8.1 General Considerations

- This section applies to both effectiveness and safety analyses when applicable.
- To account for different timing of VOLUMA XC treatment and comparable time frames of data collection and to enhance interpretability of effectiveness and safety analyses, the statistical analyses will be performed by the study periods defined in Table 2.
- For CP, effectiveness analyses and baseline characteristics will be performed on the mITT population using the as-randomized assignment.

- For TP, effectiveness and safety summaries will be performed on the VT population, using as-treated grouping.
- For MP, effectiveness and safety summaries will be performed on the VMT population.
- Study day refers to Day 1 regardless of study period (e.g., CP, TP, MT).
- The baseline for effectiveness and safety parameters will be the last non-missing assessment prior to or on Day 1, i.e., the latter of randomization or initial injection in Control Period. Day 1 is defined as the day on which the study intervention (VOLUMA XC or no-treatment) is first received.
- The change from baseline values will be computed as the postbaseline value minus the baseline values.
- For vision assessments, baseline will refer to the most-recent measurement just prior to the most-recent treatment.
- Continuous variables will be summarized by number of participants with observed values (n), mean, standard deviation (SD), median, 1st and 3rd quartiles (Q1, Q3), minimum (min), and maximum (max). Categorical variables will be summarized by the number of participants with observed values or events (n) and the percentage of participants with observed values or events.
- All statistical hypothesis tests will be performed at the 2-sided, 5% significance level, unless stated otherwise.
- All CIs will be 2-sided 95% CIs, unless stated otherwise.
- All statistical analyses will be performed using SAS Version 9.4 or subsequent.

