#### **Treatment Group Procedures: Follow-up Period**

| Procedure  | Procedure Follow-up a |         |             |          |   |
|--|----------------------------------|---------|-------------|----------|---|
|  | Month 1                          | Month 3 | Month 6     | Month 9  | Month 13 b
/Exit Visit c |
| Visit Window (Days)  | + 10                             | ± 7     | ±15         | ± 7      | ±15   |
| Urine pregnancy test d  |                                  |         |             |          | Х   |
| Weight   |                                  | Х       |             |          | Х   |
| 3D facial digital imaging  | Х                                | Х       | Х           |          | Х   |
| FACE-Q (Participant):  |                                  |         |             |          |   |
| 

Satisfaction with Facial Appearance

Satisfaction with Temples

  | х                                | Х       | Х           |          | Х   |
| Jaw Functional Limitation Scale (Participant)  | Х                                |         |             |          |   |
| Treatment Satisfaction Questions (Participant):  |                                  |         |             |          |   |
| 
 
Satisfaction with treatment
 
Natural look and feel of the results
 
How treatment met expectation
 
Likelihood of continuing the treatment
 
Willingness to recommend treatment
 
 |                                  | х       | х           |          | Х   |
| Self-perception of age (Participant)   |                                  | Х       | Х           |          | Х   |
| GAIS (Participant)   | Х                                | Х       | Х           |          | Х   |
| ATHS (EI)  | Х                                | Х       | Х           |          | Х   |
| GAIS (EI)  | Х                                | Х       | Х           |          | Х   |
| Vision Assessments: (TI or designee) 
 
Snellen visual acuity
 
Confrontational visual fields
 
Ocular motility
 
   | х                                |         |             |          |   |
| Safety telephone call  |                                  |         |             | Х        |   |
| Reason for not receiving maintenance (Participant)   |                                  |         |             |          | Х   |

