| Adverse events e (TI)   |                                  | Con     | tinuous mor | nitoring |   |
| Concomitant medications and concurrent procedures
(TI)  | Continuous monitoring            |         |             |          |   |

a month = 30 days

a The follow-up visit schedule is based on the date of the last study intervention (ie, if no touch-up treatment is performed, the Month 1 visit occurs 30 days after initial treatment; if touch-up treatment is performed, the Month 1 visit occurs 30 days after touch-up treatment).

b At the Month 13 visit, participants will be offered a maintenance treatment after completion of the Month 13 visit. Participants who accept maintenance treatment will undergo the additional procedures specified in Table 1-4. Participants who do not accept maintenance treatment will exit the study after the Month 13 procedures are completed.

c If a participant withdraws for any reason prior to the final study visit, attempts will be made to perform assessments at an exit visit.

d For female participants of childbearing potential. A female is not considered of childbearing potential if she has been postmenopausal for at least 1 year or does not have a uterus at the time of study entry.

e Will include a general, nondirected question about vision symptoms.

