#### UVEDERM VOLUMA° XC injectable gel

| Table 1-4 Tre  | eatment Grou                                   | p Procedures                             | s: Maintenan                                 | ce Treatment                                 | and Follow-u                                 | ıp Period  |
|--|--|--|--|--|--|--|
| Procedure  | Main   | tenance Trea                             | Follow-up                        | )  |  |  |
|  | Maintenance
Treatment a
Visit | 3 Days After
Maintenance
Treatment | 14 Days
After
Maintenance
Treatment | Month 1
After
Maintenance
Treatment | Month 3
After
Maintenance
Treatment | Month 6 After
Maintenance
Treatment/Exit
Visit c |
| Visit Window (Days)  |  | ± 2                                      | + 4  | + 10   | ± 7  | ± 15   |
| Urine pregnancy test d  | Xe   |  |  |  |  | X  |
| 3D facial digital imaging  | Xf   |  | Х  | Х  | Х  | Х  |
| Vision Assessments: (TI or   |  |  |  |  |  |  |
| designee)  |  |  |  |  |  |  |
| 

Snellen visual acuity

Confrontational visual fields

  | X g                                 |  | х  | х  |  |  |
| 
 
Ocular motility
 
  |  |  |  |  |  |  |
| Study intervention,
intervention characteristics
(TI)  | х  |  |  |  |  |  |
| Procedural pain (Participant)  | Х  |  |  |  |  |  |
| Safety telephone call (TI)   |  | Х  |  |  |  |  |
| Safety e-diaryh (Participant)  |  | Continuous                               |  |  |  |  |
| FACE-Q (Participant)   |  |  |  |  |  |  |
| 
 
Satisfaction with Facial
Appearance
 
Satisfaction with
Temples
 
   |  |  |  | х  | х  | х  |
| Treatment Satisfaction
Questions (Participant):   |  |  |  |  |  |  |
| 
 
Satisfaction with
treatment
 
Natural look and feel of
the results
 
How treatment met
expectation
 
 |  |  |  | Х  | X  | Х  |
| 

Likelihood of continuing
the treatment

Willingness to
recommend treatment

                                      |  |  |  |  |  |  |
| Self-perception of age
(Participant)  |  |  |  | Х  | Х  | Х  |
| Jaw Functional Limitation
Scale (Participant)   |  |  | х  | х  |  |  |
| GAIS (Participant)   |  |  |  | Х  | Х  | Х  |
| ATHS (EI)  |  |  |  | Х  | Х  | Х  |
| GAIS (EI)  |  |  |  | Х  | Х  | Х  |

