| Adverse events i  |  |  | Continuou                                    | is monitoring                                |  |  |
| Concomitant medications and concurrent procedures  |  |  | Continuou                                    | s monitoring                                 |  |  |

- a A maintenance treatment is offered to participants who complete the Month 13 visit. The procedures must occur no later than 14 days after the Month 13 visit.
- b Follow-up visit schedule is based on the date of the last study intervention (ie, maintenance treatment).
- c If a participant withdraws for any reason prior to the final study visit, attempts will be made to perform assessments at an exit visit.
- d For female participants of childbearing potential. A female is not considered of childbearing potential if she has been postmenopausal for at least 1 year or does not have a uterus at the time of study entry.
- e Administered and confirmed negative prior to study intervention. If maintenance treatment is done on the same day of the Month 13 visit, this assessment does not need to be repeated.
- f Prior to maintenance treatment. If maintenance treatment is done on the same day of the Month 13 visit, this assessment does not need to be repeated.
- g Vision assessments will be performed by TI (or designee) before study intervention and at least 30 minutes after completing the injection procedures.
- h The safety e-diaries are to be completed following each study intervention starting on the day of treatment.
- i Will include a general, nondirected question about vision symptoms.

a month = 30 days

#### Protocol 1878-702-008 Amendment 2

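### No jaw function score is scheduled within about 11 months before the maintenance injection, so the post-maintenance scores have no recent pre-injection reference

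*SAP*

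**What the plan says.** SAP 3.4 lists jaw function assessment among the safety endpoints. SAP 9.1 plans maintenance-period safety summaries on the participants who received maintenance treatment.

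In the protocol's schedules, the row beginning "Jaw Functional Limitation Scale (Participant" is marked as follows for the treatment group:

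- Table 1-2 (treatment period): before the initial injection, 14 days after it, at the 30-day/touch-up visit, and 14 days after touch-up.
- Table 1-3 (follow-up): Month 1 only. Months 3, 6, 9 and 13 are blank.
- Table 1-4 (maintenance): 14 days and Month 1 after maintenance. The maintenance treatment visit is blank.

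SAP 8.1 gives one general baseline rule: "The baseline for effectiveness and safety parameters will be the last non-missing assessment prior to or on Day 1". Day 1 is the day the study intervention is first received, and study day is counted from it in every period. The one exception visible in that section is: "For vision assessments, baseline will refer to the most-recent measurement just prior to the most-recent treatment". The protocol supplies the data for that exception. For the maintenance visit, Table 1-4 footnote g says: "Vision assessments will be performed by TI (or designee) before study intervention and at least 30 minutes after completing the injection procedures".

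**The concern.** The maintenance period is where the study learns about the safety of a repeat injection. A score taken after that injection can be read as change only against a score taken shortly before it. For the JFLS, none is scheduled. A participant whose jaw function worsened during the year between the first cycle and maintenance, for any reason, would look the same on the JFLS as one whose jaw function worsened after maintenance.

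The Day 1 baseline rule adds to the problem. If it governs the JFLS, change in the maintenance period combines the first cycle, the following year and the maintenance injection. Exclusion criterion 1.07 removes people with temporomandibular or other jaw problems at entry, so Day 1 scores are likely to be low, and the more likely error is apparent worsening.

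**Working it through.** **Inputs**

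- Length of a month: "a month = 30 days" (Table 1-3), so Month 13 is 13 × 30 = 390 days.
- Month 13 window: ±15 days (Table 1-3), so 375 to 405 days after the last treatment.
- Anchor of the follow-up schedule: the last study intervention. Table 1-3 footnote a says "if touch-up treatment is performed, the Month 1 visit occurs 30 days after touch-up treatment".
- Touch-up: 30 days after initial treatment, window +10 (Table 1-2), so day 30 to 40.
- Month 1 visit: window +10 (Table 1-3), so 30 to 40 days after the last treatment.
- Maintenance: 0 to 14 days after the Month 13 visit (Table 1-4 footnote a).
- Post-maintenance JFLS: 14 days (+4) and Month 1 (+10) after maintenance (Table 1-4).

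**The plan's own timeline.** Protocol 4.1 gives up to 21 months for the treatment group: 1 (screening) + 1 (treatment) + 13 (follow-up) + 6 (maintenance follow-up) = 21. This reproduces at nominal timing. The documents do not state the age of the JFLS baseline.

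**Last treatment to maintenance.** Earliest 390 − 15 + 0 = 375 days. Latest 390 + 15 + 14 = 419 days.

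**Day 1 to maintenance**

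- Without touch-up: 375 to 419 days.
- With touch-up: 30 + 375 = 405 days to 40 + 419 = 459 days.
- Overall: 375 to 459 days.

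**Latest scheduled JFLS to maintenance.** This is the Month 1 score: 375 − 40 = 335 days to 419 − 30 = 389 days.

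**Age of the Day 1 score at the post-maintenance readings**

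- 14-day visit: 375 + 14 = 389 days to 459 + 18 = 477 days.
- Month 1 visit: 375 + 30 = 405 days to 459 + 40 = 499 days.
- Overall: 389 to 499 days.

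**Would a change to the SAP alone be enough?** No. If the baseline became the last score before the most recent treatment, as for vision, it would still reach back 335 to 389 days. A score taken at the maintenance visit before injection would be 0 days old.

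**The case against.** Four points on the other side have weight.

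1. *The analysis is inferred.* A reader might infer that the SAP plans to report JFLS change from Day 1 in the maintenance period. No visible passage says so. The SAP contents list a section 9.10 on other safety analyses, whose opening is missing from the text available and which may hold redacted lines. SAP 8.1 applies to safety only where applicable. This stands, so the Day 1 baseline part of the point is conditional. The schedule gap does not depend on it.

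2. *The plan does not insist on a pre-injection JFLS before every repeat injection.* At the touch-up visit the JFLS carries no before-treatment footnote in Table 1-2 or Table 1-6, while 3D imaging does. Pre-injection JFLS is explicit only before a first exposure: initial treatment in Table 1-2 and the control group's optional treatment in Table 1-6. This is fair, and only vision is explicitly re-measured before every injection. But at touch-up there is a JFLS at that visit and another 14 to 18 days after the initial injection, so 30 − 18 = 12 to 40 − 14 = 26 days before touch-up. The gap before maintenance is about a year.

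3. *Attribution does not rest on the JFLS.* A reader might infer that jaw problems after maintenance could not be attributed at all. The documents do not support that. Adverse events are monitored continuously, the investigator assesses causality with regard to timing and alternative causes (protocol 10.7.4), and SAP 9.2.2 sets maintenance-period events beside those of the first 6 months. A jaw problem reported at Month 8 would carry an onset date before maintenance. What remains uncovered is change on the scale that was not reported as an event.

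4. *Change from Day 1 is a legitimate summary.* It describes cumulative change from the pre-exposure state. That stands, and it is a reason to keep it as a supplement. It answers a different question from change over the maintenance injection.

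**Conclusion.** The schedule gap is established from the protocol tables alone: no JFLS at Month 13 or at the maintenance visit, and the nearest scheduled earlier score 335 to 389 days before the injection. It affects every participant who receives maintenance treatment. If the general rule in SAP 8.1 applies to the JFLS, the baseline is 375 to 459 days old at injection and 389 to 499 days old when the post-maintenance scores are taken. These ranges assume visits within window.

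The consequence is limited to the JFLS: on that scale, limitation arising in the intervening year cannot be told apart from change after maintenance. No size of bias in a mean JFLS change can be given, because the documents contain no rate at which jaw limitation arises over that year. No visible test or decision rule uses the JFLS, so the effectiveness conclusion is not touched. This is a modest gap in the repeat-treatment safety data, worth closing because it is cheap to close.

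**What to change.** - **Protocol Table 1-4:** add the JFLS at the maintenance treatment visit, completed before study intervention. Placing it here limits it to participants who accept maintenance. It should not rely on a Month 13 score, because none is scheduled.
- **SAP 8.1:** extend the vision sentence so that, for the maintenance period, the JFLS baseline is this pre-maintenance score. Keep change from Day 1 as a supplementary cumulative summary. If redacted text already sets a JFLS baseline, align it with this.
- **Participants already treated without the score:** report their post-maintenance JFLS as observed values, and do not present change from Day 1 as an effect of maintenance.

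The cost is a few minutes of participant time at an existing visit, one SAP sentence and a minor protocol amendment. It recovers nothing for those already treated, and the maintenance comparison remains before-after without a concurrent control.
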